7.1.4 Response Criteria

7.1.4.1 Evaluation of Target Lesions

Response and progression will be evaluated in this study using the international criteria proposed by the Response Evaluation Criteria in Solid Tumors (RECIST) version 1.1.

Complete Response (CR): Disappearance of all target lesions. There can be no appearance of new lesions. Any pathological lymph nodes must have reduction in short axis to < 10 mm.

Partial Response (PR): At least a 30% decrease in the sum of target lesions, taking as reference the baseline sum diameters. There can be no appearance of new lesions.

Progressive Disease (PD): At least a 20% increase in the sum of the diameters of target lesions, taking as reference the smallest sum on study (this includes the baseline sum if that is the smallest on study). The appearance of one or more new lesions is also considered progression).

Stable Disease (SD): Neither sufficient shrinkage to qualify for PR nor sufficient increase to qualify for PD, taking as reference the smallest sum diameters while on study.

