5.1.2 Phase II

The phase II portion will consist of patients with ES-SCLC who completed platinum based standard first-line chemotherapy (e.g. 4-6 cycles of platinum plus etoposide or irinotecan) without disease progression (responders plus stable disease) at the time of initiation of the combination therapy with $^{177}\text{Lu-DOTA}^0\text{-Tyr}^3\text{-Octreotate}$ and nivolumab. Eligible patients will then be randomly allocated in two arms: one will be treated with the combination of $^{177}\text{Lu-DOTA}^0\text{-Tyr}^3\text{-}$

Octreotate and nivolumab, and the other arm will continue be followed (observation) after completion the standard chemotherapy treatment.

Randomization:

Patients who do not receive radiotherapy after chemotherapy

- The randomization must occur within 6 weeks of the last chemotherapy cycle.
- The study treatment must start within 2 weeks from randomization, but no less than 2 weeks from last dose of chemotherapy.

Patients who receive radiotherapy (including prophylactic cranial radiation and/or thoracic radiation) after chemotherapy

- Randomization must occur at least 8 weeks after completion of radiation therapy but within 12 weeks after completion of radiation therapy.

Randomization process:

- OnCore will be used as statistical center and the randomization algorithm will be developed by the study biostatistician.
- The project management department will be the first point of contact for assessment through email.

Courses are defined as 56 days of dosing. Nivolumab will be given until progressive disease, patient withdrawal, or toxicities. For patients randomized to the observation group, cross-over at the time of disease progression will be allowed, since the primary endpoint is PFS and not OS.

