7.1.2 Disease Parameters

Measurable disease: Measurable lesions are defined as those that can be accurately measured in at least one dimension (longest diameter to be recorded) as ≥ 20 mm by chest x-ray, as ≥ 10 mm with CT scan, or 10 mm with calipers by clinical exam. All tumor measurements must be recorded in millimeters (or decimal fractions of centimeters).

Note: Tumor lesions that are located in a previously irradiated area might or might not be considered measurable at the discretion of the PI.

Malignant lymph nodes: To be considered pathologically enlarged and measurable, a lymph node must be ≥ 15 mm in short axis when assessed by CT scan (CT scan slice thickness recommended to be no greater than 5 mm). At baseline and in follow-up, only the short axis will be measured and followed.

Non-measurable disease: All other lesions (or sites of disease), including small lesions (longest diameter < 10 mm or pathological lymph nodes with ≥ 10 to < 15 mm short axis), are considered non-measurable disease. Bone lesions, leptomeningeal disease, ascites, pleural/pericardial effusions, lymphangitis cutis/pulmonis, inflammatory breast disease, abdominal masses (not followed by CT or MRI), and cystic lesions are all non-measurable.

Note: Cystic lesions that meet the criteria for radiographically defined simple cysts should not be considered as malignant lesions (neither measurable nor nonmeasurable) since they are, by definition, simple cysts.

'Cystic lesions' thought to represent cystic metastases can be considered as measurable lesions, if they meet the definition of measurability described above. However, if non-cystic lesions are present in the same patient, these are preferred for selection as target lesions.

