Target lesions: All measurable lesions up to a maximum of 2 lesions per organ and 5 lesions in total, representative of all involved organs, should be identified as **target lesions** and recorded and measured at baseline. Target lesions should be selected on the basis of their size (lesions with the longest diameter), be representative of all involved organs, and their suitability for accurate repeated measurements (either by imaging techniques or clinically). A sum of the diameters (longest for non-nodal lesions, short axis for nodal lesions) for all target lesions will be calculated and reported as the baseline sum diameters. If lymph nodes are to be included in the sum, then only the short axis is added into the sum. The baseline sum diameters will be used as reference to further characterize any objective tumor regression in the measurable dimension of the disease.

Non-target lesions. All other lesions (or sites of disease) including any measurable lesions over and above the 6 target lesions should be identified as **non-target lesions** and should also be recorded at baseline. Measurements of these lesions are not required, but the presence or absence of each should be noted throughout follow-up.

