7.1.3 Methods for Evaluation of Measurable Disease

All measurements should be taken and recorded in metric notation using a ruler or calipers. All baseline evaluations should be performed as closely as possible to the beginning of treatment and never more than 28 days before the beginning of the treatment.

The same method of assessment and the same technique should be used to characterize each identified and reported lesion at baseline and during follow-up. Imaging-based evaluation is preferred to evaluation by clinical examination unless the lesion(s) being followed cannot be imaged but are assessable by clinical exam.

Clinical lesions: Clinical lesions will only be considered measurable when they are superficial (e.g., skin nodules and palpable lymph nodes) and ≥ 10 mm diameter as assessed using calipers (e.g., skin nodules). In the case of skin lesions, documentation by color photography, including a ruler to estimate the size of the lesion, is recommended.

Conventional CT and MRI: CT and MRI - CT and MRI are the best currently available and reproducible methods to measure target lesions selected for response assessment. For this study helical multidetector CT will be performed with cuts of 5 mm in slice thickness for chest, abdomen and pelvis lesions and 2-3 mm thickness for head and neck lesions. For consistency, it is recommended that investigators use the same imaging modality for follow-up of tumors for a given patient.

Cytology, Histology: These techniques can be used to differentiate between partial responses (PR) and complete responses (CR) in rare cases.

The cytological confirmation of the neoplastic origin of any effusion that appears or worsens during treatment when the measurable tumor has met criteria for response or stable disease is mandatory to differentiate between response or stable disease (an effusion may be a side effect of the treatment) and progressive disease.

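### The printed target-lesion progression rule sets no minimum absolute increase, so when the nadir sum is small (below 25 mm) measurement variation alone can produce PFS events

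*Combined protocol and SAP*

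**What the plan says.** Section 7.1.4.1 of the combined protocol and SAP defines progression in target lesions as "At least a 20% increase in the sum of the diameters of target lesions, taking as reference the smallest sum on study"; one or more new lesions also count. It gives no minimum increase in millimetres, and none appears elsewhere in section 7. The same section and section 7.1 name "Response Evaluation Criteria in Solid Tumors (RECIST) version 1.1" as the criteria, but do not reproduce them or say which text prevails if the two differ.

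Other provisions that matter here:

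- **Smallest target.** Section 7.1.2 makes a non-nodal lesion measurable from "10 mm with CT scan"; a node needs a 15 mm short axis.
- **What is compared.** The rule acts on a sum: the diameters "for all target lesions will be calculated and reported as the baseline sum diameters", over at most five lesions.
- **Imaging.** In section 7.1.3, "helical multidetector CT will be performed with cuts of 5 mm in slice thickness for chest, abdomen and pelvis lesions". Section 6.2 schedules imaging every 8 weeks in both arms.
- **Population.** Phase II patients have finished first-line chemotherapy "without disease progression (responders plus stable disease") (section 5.1.2).
- **Endpoint.** Sections 7.1.6 and 11.3 count progression or death as the PFS event.
- **Confirmation.** Later confirmation is mentioned for progression in non-target lesions only (7.1.4.2), and a new FDG-PET finding needs CT support (7.1.3). Nothing similar is specified for target-lesion progression.

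**The concern.** A purely relative threshold shrinks with the tumour. If the smallest sum is 10 mm, a reading of 12 mm is progression. The reference is the lowest reading so far, so one low reading lowers the bar for every later scan, and the chance of a false call builds up over time.

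PFS is the phase II primary endpoint, the trial is open-label, and only 40 events are planned. A false progression is a false event. If false events arise equally in both arms, they pull the hazard ratio towards 1 and cost power.

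They also have consequences for patients. Progression makes an observation patient eligible for cross-over (5.1.2, 11.1). For treated patients the text is not uniform: 5.1.2 and 5.2.2 give nivolumab until progression, while 5.5 allows treatment beyond it.

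**Working it through.** **1. The plan's own figure.** Section 11.2 assumes medians of 2 and 5 months (HR 0.4), two-sided 0.05 and 80% power, and states 40 events, 44 patients, and 52 with 15% dropout. The allocation ratio is not stated; I assume 1:1.

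- Schoenfeld: 4 × (1.960 + 0.842)² / (ln 0.4)² = 37.4, so 38 events.
- Freedman: (1.4 / 0.6)² × (1.960 + 0.842)² = 42.7, so 43 events.
- Power at 40 events (Schoenfeld): Φ(√40 / 2 × 0.916 − 1.960) = Φ(0.938) = 82.6%.
- 44 / 0.85 = 51.8, so 52 patients.

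The stated 40 lies between the two formulas. The sample size is not in dispute.

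**2. The trigger in millimetres.** It is 20% of the nadir sum. The 5 mm minimum is illustrative.

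| Nadir sum | 20% rule | 20% and at least 5 mm |
|---|---|---|
| 10 mm | 2 mm | 5 mm |
| 15 mm | 3 mm | 5 mm |
| 20 mm | 4 mm | 5 mm |
| 25 mm | 5 mm | 5 mm |
| 50 mm | 10 mm | 10 mm |

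A 5 mm minimum binds only where 0.2 × nadir is below 5 mm, that is, below 25 mm.

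**3. False progression at one scan, no true growth.** Let S be the true size of a sole target lesion, and let baseline m0 and follow-up m1 have independent normal errors with SD s. The documents give no reading error, so s is assumed. Then m1 − 1.2 × m0 has mean −0.2S and SD s√(1 + 1.44), and the probability that m1 is at least 1.2 × m0 is Φ(−0.2S / 1.562s). For S = 10 mm:

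- s = 0.75 mm: Φ(−1.71) = 4.4%
- s = 1.0 mm: Φ(−1.28) = 10.0%
- s = 1.5 mm: Φ(−0.85) = 19.7%

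**4. Cumulative false progression with the running nadir.** This is a simulation of a baseline and three follow-up scans in 400,000 stable patients.

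| Sole lesion, by third scan | s = 0.75 mm | s = 1.0 mm | s = 1.5 mm |
|---|---|---|---|
| 10 mm, rule as printed | 19% | 37% | 61% |
| 10 mm, with 5 mm minimum | <0.1% | 0.1% | 4.7% |
| 15 mm, rule as printed | 3% | 13% | 37% |

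Rounding readings to whole millimetres raises the printed-rule figures. At 10 mm and s = 1.0 mm they become 15% at the first scan and 49% by the third.

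**5. Larger sums.** For a 50 mm sum of two lesions, first-scan false progression is at most 1.3% for s up to 2 mm, with or without the minimum. For 100 mm over five lesions it is at most 0.2%.

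**6. Trial level.** Suppose false progression averages f per scan over all patients, equally in both arms. Scans are 56 days (1.84 months) apart, so the added hazard is λf = −ln(1 − f) / 1.84. With λC = ln 2 / 2 = 0.347 and λT = ln 2 / 5 = 0.139, the observed HR is (λT + λf) / (λC + λf).

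| f (assumed) | λf | Observed HR | Power at 40 events |
|---|---|---|---|
| 0 | 0 | 0.40 | 82.6% |
| 2% | 0.011 | 0.42 | 79% |
| 5% | 0.028 | 0.44 | 73% |
| 10% | 0.057 | 0.49 | 63% |

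To read f against step 3: at s = 1.0 mm, an average of 2% needs about 2 / 10 = 20% of patients to have a sole 10 mm lesion. At s = 1.5 mm, an average of 10% needs about 10 / 20 = 50%. The lower part of the range is easier to reach than the upper.

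**The case against.** **RECIST 1.1 may already supply a minimum.** The protocol says progression will be evaluated by that standard, whose text is not in the documents. A reader might infer that the protocol departs from the standard, or that no minimum applies at all. The documents support neither; they show only that the printed rule omits one and that precedence is unstated. The omission still matters, because sites will read the printed rule and the printed summary is not reliable elsewhere: section 7.1.2 caps target lesions at five, then treats those beyond six as non-target.

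**The 10 mm case is extreme.** This stands. A reader might infer that 2 mm of growth in any 10 mm lesion is progression. It is so only if that lesion is the whole nadir sum. At 20 mm, first-scan false progression is 0.03%, 0.5% or 4.4% for the same SDs. Nor can one infer that small sums are common: post-chemotherapy entry makes them plausible, but no baseline sums are given.

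**Slice thickness is not reading error.** This also stands. Nothing in the documents equates the 5 mm cuts with diameter error, so a 2 mm change is not shown to be noise on that ground. The 5 mm value is a candidate, not a derivation.

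**Three scans without growth is a long time here.** With exponential PFS at the planned medians, 15% of controls and 47% of treated patients would be progression-free at 24 weeks (5.52 months: 2^(−5.52/2) and 2^(−5.52/5)). The third-scan figures therefore describe patients who stay stable, not the whole trial.

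**The error is the same in both arms.** A reader might infer bias in favour of the treatment. Equal noise dilutes the effect instead. Open-label reading could add bias, but that was not quantified. Nor does false progression automatically end treatment, given section 5.5.

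**Conclusion.** The concern holds for the rule as printed. Section 7.1.4.1 lets a small sum progress on a rise of a few millimetres, and nothing specified afterwards checks that call for target lesions. The effect is confined to nadir sums below 25 mm for any 5 mm minimum, and it is steepest near 10 mm.

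The patient-level figures rest on assumed SDs of 0.75 to 1.5 mm, independent normal errors and no true growth. The trial-level range, HR 0.42 to 0.49 and power 79% to 63%, also rests on an assumed average false-progression rate of 2% to 10% per scan, constant over time and equal in both arms. Where in that range the trial falls, or whether it falls below it, depends on the unknown share of small sums. This is a definition to correct before PFS is analysed; it does not invalidate the design.

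**What to change.** In section 7.1.4.1, add that the sum must also rise by a stated minimum absolute amount, for example 5 mm. Check the wording against the RECIST 1.1 reference the protocol cites, and state in 7.1.4.1 and 11.3 that this definition governs PFS. Correct the five-versus-six target-lesion count in 7.1.2 at the same time. Sections 5.1.2, 5.2.2 and 5.5 must also be reconciled on treatment after progression.

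The cost is one clause and an amendment. A few true progressions in small tumours would be dated one scan (8 weeks) later, under the same rule in both arms. Sums of 25 mm or more are unaffected.

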7.1.4.2 Evaluation of Non-Target Lesions

Complete Response (CR): Disappearance of all non-target lesions and normalization of tumor marker level. All lymph nodes must be non-pathological in size (<10 mm short axis).

Non-CR/Non-PD: Persistence of one or more non-target lesion(s) and/or maintenance of tumor marker level above the normal limits.

Progressive Disease (PD): Appearance of one or more new lesions and/or unequivocal progression of existing non-target lesions. Unequivocal progression should not normally trump target lesion status. It must be representative of overall disease status change, not a single lesion increase.

Although a clear progression of “non-target” lesions only is exceptional, the opinion of the treating physician should prevail in such circumstances, and the progression status should be confirmed at a later time by the review panel (or Principal Investigator).

7.1.4.3 Evaluation of Best Overall Response

The best overall response is the best response recorded from the start of the treatment until disease progression/recurrence (taking as reference for progressive disease the smallest measurements recorded since the treatment started). The patient's best response assignment will depend on the achievement of both measurement and confirmation criteria.

Table 7. Evaluation of patients with measureable disease.

Target Lesions	Non-Target Lesions	New Lesions*	Overall Response
CR	CR	No	CR
CR	Non-CR/Non-PD	No	PR
CR	Not evaluated	No	PR
PR	Non-CR/Non-PD/not evaluated	No	PR
SD	Non-CR/Non-PD/not evaluated	No	SD
PD	Any	Yes or No	PD
Any	PD**	Yes or No	PD
Any	Any	Yes	PD

* See RECIST 1.1 manuscript for further details on what is evidence of a new lesion.

****** In exceptional circumstances, unequivocal progression in non-target lesions may be accepted as disease progression.

Note: Patients with a global deterioration of health status requiring discontinuation of treatment without objective evidence of disease progression at that time should be reported as “symptomatic deterioration”. Every effort should be made to document the objective progression even after discontinuation of treatment.

Table 8. Evaluation of patients with non-measurable disease

Non-Target Lesions	New Lesions	Overall Response
CR	No	CR
Non-CR/non-PD	No	Non-CR/non-PD*
Not all evaluated	No	Not evaluated
Unequivocal PD	Yes or No	PD
Any	Yes	PD
* ‘Non-CR/non-PD’ is preferred over ‘stable disease’ for non-target disease since SD is increasingly used as an endpoint for assessment of efficacy in some trials so to assign this category when no lesions can be measured is not advised.		

7.1.5 Duration of Response

Duration of overall response: The duration of overall response is measured from the time measurement criteria are met for CR or PR (whichever is first recorded) until the first date that recurrent or progressive disease is objectively documented (taking as reference for progressive disease the smallest measurements recorded since the treatment started).

The duration of overall CR is measured from the time measurement criteria are first met for CR until the first date that recurrent disease is objectively documented.

Duration of stable disease: Stable disease is measured from randomization until the criteria for progression are met, taking as reference the smallest measurements recorded since the treatment started.

7.1.6 Progression-Free Survival

PFS is defined as the duration of time from randomization to time of progression or death, whichever occurs first.

7.1.7 Overall Survival

Overall survival is defined as the duration of time from randomization to death from any cause.

8.0 ADVERSE EVENTS

8.1 Definitions

8.1.1 Definition of Adverse Event

An adverse event (AE) is any untoward medical occurrence in a patient receiving study treatment and which does not necessarily have a causal relationship with this treatment. An AE can therefore be any unfavorable and unintended sign (including an abnormal laboratory finding), symptom, or disease temporally associated with the use of an experimental intervention, whether or not related to the intervention. For this study, AEs will include events reported by the patient, as well as clinically significant abnormal findings on physical examination or laboratory evaluation. A new illness, symptom, sign or clinically significant laboratory abnormality or worsening of a pre-existing condition or abnormality is considered an AE. All AEs must be recorded on the AE case report form.

AEs should be reported up to 30 days following the last dose of study drug. All AEs, including clinically significant abnormal findings on laboratory evaluations, regardless of severity, will be followed until satisfactory resolution. AEs should be reported up to 30 days following the last dose of study drug.

An abnormal laboratory value will be considered an AE if the laboratory abnormality is characterized by any of the following:

- Results in discontinuation from the study
- Is associated with clinical signs or symptoms
- Requires treatment or any other therapeutic intervention
- Is associated with death or another serious adverse event, including hospitalization.
- Is judged by the Investigator to be of significant clinical impact
- If any abnormal laboratory result is considered clinically significant, the investigator will provide details about the action taken with respect to the test drug and about the patient's outcome.

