6.2 Procedures During Treatment

Patients receiving study treatment will be followed every 2 weeks and the following will be done (unless otherwise indicated).

- History and physical exam (\pm 3 days).
- Laboratory evaluation (\pm 3 days): Hematologic profile (CBC with differential). Biochemical profile. Does not need to repeat for C1D1 if performed within 7 days.
- Thyroid function testing will be done every cycle on day 1 (\pm 3 days) and day 29 (\pm 3 days) for subjects receiving nivolumab. Does not need to repeat on C1D1.
- Tumor imaging will be performed every 8 weeks (\pm 7 days).
- NETSPOT[®] PET scan on cycle 2 day 1 (\pm 3 days) to assess the metabolic response.
- Serum or urine beta-hCG for female patients of childbearing age within 24 hours prior to the administration of ¹⁷⁷Lu-DOTA⁰-Tyr³-Octreotate.

Patients randomized to observation will be followed every 4 weeks and the following will be done.

- History and physical exam (\pm 3 days).
- Laboratory evaluation (\pm 3 days): Hematologic and biochemical profile. Laboratory evaluation can be performed within 3 days prior to clinic visit.
- Tumor imaging will be performed every 8 weeks (\pm 7 days).

After 30 days (\pm 7 days) from treatment termination, the following will be obtained if the patient is available:

- History and physical exam.
- Laboratory evaluation: Hematologic and biochemical profile. Thyroid function testing.

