8.3 Reporting Requirements for Adverse Events

Participating investigators (all sites) must report all serious adverse events to the Sponsor-Investigator within **24 hours** of discovery or notification of the event. The participating investigator must also provide follow-up information on the SAE until final resolution. The Sponsor-Investigator can be contacted at [name], E-mail: [contact], [contact] with CC to [contact] and CC to sub-investigator [name], E-mail: [contact].

The Sponsor-Investigator will review the SAE and report the event to the FDA, external collaborator(s), IND manufacturer, and IRB as applicable as described below.

It is the Sponsor-Investigator's responsibility (e.g. lead site PI) to ensure that all serious adverse events that occur on the study (e.g. all SAEs that occur at each enrolling institution) are reported to all participating sites.

*After informed consent has been obtained but prior to initiation of study treatment, only serious adverse events caused by a protocol-mandated intervention (e.g., invasive procedures such as biopsies) should be reported.

**After initiation of study treatment, all adverse events will be reported until 30 days after the last dose of study treatment or last observation follow-up visit or until initiation of new systemic anti-cancer therapy, whichever occurs first, and serious adverse events will continue to be reported until 90 days after the last dose of study treatment or last observation follow-up visit or until initiation of new systemic anti-cancer therapy, whichever occurs first.

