11.3 Data Analyses Plans

PFS will be defined as the time from random assignment to disease progression or death from any cause, whichever comes first. OS will be defined as the time from random assignment to death from any cause; living patients will be censored at the date of last follow-up. Survival will be estimated and plotted by the Kaplan–Meier method. In addition, the median progression-free and overall survival times will be reported along with the 95% confidence intervals. The cox proportional hazards regression model will be used to obtain hazard ratios (HRs) and the log-rank test will be utilized to compare survival estimates between the maintenance group and the control observation group. Secondary endpoints will be analyzed when the required number of events for the primary endpoint (PFS) has been met. The DCR is defined as the proportion of patients with a best overall response of CR, PR, or SD. The ORR is defined as the proportion of patients with a best overall response of CR or PR. All randomized subjects will consist of the safety population. This population will be used for all summaries of safety data (AEs, concomitant medications, laboratory data). P-values less than 0.05 will be considered significant. All statistical analyses will be performed using SAS (Version 9.4; SAS Institute, Cary, NC). [name] will serve as the study statistician.

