The collection of nonserious AE information should begin at initiation of study drug. All nonserious adverse events (not only those deemed to be treatment-related) should be collected continuously during the treatment period and for a minimum of 100 days following the last dose of study treatment. Nonserious AEs should be followed to resolution or stabilization, or reported as SAEs if they become serious. Follow-up is also required for nonserious AEs that cause interruption or discontinuation of study drug and for those present at the end of study treatment as appropriate.

Laboratory Test Abnormalities

All laboratory test results captured as part of the study should be recorded following institutional procedures. Test results that constitute SAEs should be documented and reported as such. The following laboratory abnormalities should be documented and reported appropriately:

- Any laboratory test result that is clinically significant or meets the definition of an SAE
- Any laboratory abnormality that required the subject to have study drug discontinued or interrupted
- Any laboratory abnormality that required the subject to receive specific corrective therapy.

Pregnancy

If, following initiation of the investigational product, it is subsequently discovered that a study subject is pregnant or may have been pregnant at the time of investigational product exposure, including during at least 6 half lives after product administration, the investigational product will be permanently discontinued in an appropriate manner (e.g. dose tapering if necessary for subject safety). The investigator must immediately notify Worldwide Safety @BMS of this event via the Pregnancy Surveillance Form in accordance with SAE reporting procedures. Follow-up information regarding the course of the pregnancy, including perinatal and neonatal outcome and, where applicable, offspring information must be reported on the Pregnancy Surveillance Form

[provided upon request from BMS]. Any pregnancy that occurs in a female partner of a male study participant should be reported to BMS. Information on this pregnancy will be collected on the Pregnancy Surveillance Form.

Overdose

An overdose is defined as the accidental or intentional administration of any dose of a product that is considered both excessive and medically important. All occurrences of overdose must be reported as an SAE.

Other Safety Considerations

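### The adverse-event rules for the phase II observation arm contradict each other: collection is tied to study treatment, yet every randomized patient is in the safety population

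*Combined protocol and SAP*

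**What the plan says.** Several provisions tie AE collection to treatment:

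- Section 8.1.1 defines the event: "An adverse event (AE) is any untoward medical occurrence in a patient receiving study treatment". It closes the window by the last dose: "AEs should be reported up to 30 days following the last dose of study drug".
- Section 8.3 restricts what is reported before treatment: "After informed consent has been obtained but prior to initiation of study treatment, only serious adverse events caused by a protocol-mandated intervention". Full reporting then begins: "After initiation of study treatment, all adverse events will be reported until 30 days after the last dose of study treatment".
- Appendix E, on non-serious events: "The collection of nonserious AE information should begin at initiation of study drug".
- Sections 5.3.1 and 7.1.1 make patients evaluable for toxicity by virtue of having been treated, in 7.1.1 from first treatment onward.

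Other provisions assume that observation patients contribute:

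- Section 8.3 gives reporting an end that fits an untreated patient: "all adverse events will be reported until 30 days after the last dose of study treatment or last observation follow-up visit". The same alternative appears in its 90-day SAE rule.
- Appendix E collects all SAEs, related or not, once consent is signed.
- Section 11.3: "All randomized subjects will consist of the safety population". That population serves every summary of AEs, concomitant medications and laboratory data. The section does not say whether summaries are by arm or pooled, or where events after cross-over are counted.

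On visits, section 6.2 says: "Patients randomized to observation will be followed every 4 weeks and the following will be done". The list is history and examination, laboratory tests, and imaging every 8 weeks. The study calendar (Appendix D) has a row for AE assessment, but its columns cover treatment cycles, end of treatment and follow-up, with no observation schedule. Sections 5.1.2 and 11.1 allow cross-over at progression.

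**The concern.** A patient on observation has no treatment start and no last dose unless they cross over. Under the treatment-based rules, that patient stays in the pre-treatment state of section 8.3, where only procedure-caused SAEs are reportable. Under section 11.3, the same patient is in the denominator of every AE table.

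This matters because safety of the combination is a secondary objective in phase II (section 3.3.1) and part of the hypothesis (section 3.1). Background events are plausible in this population. Section 4.2.1.5 allows randomization within 6 weeks of the last chemotherapy cycle, or 8 to 12 weeks after radiotherapy. Section 4.2.1.3 accepts residual grade 1 toxicity and grade 2 platinum neuropathy. The observation arm is the trial's only concurrent measure of what disease and earlier treatment produce by themselves. If its events are recorded incompletely, or differently across the 6 to 7 planned institutions, that measure is lost and cannot be reliably rebuilt afterwards.

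**Working it through.** **Step 1. The plan's denominator.** Section 11.2 gives 44 patients before dropout and 15% dropout: 44 / (1 − 0.15) = 51.8, rounded up to 52. This reproduces the stated 52. The allocation ratio is not stated; at an assumed 1:1, each arm has 52 / 2 = 26.

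**Step 2. The rules side by side, for an observation patient before cross-over.**

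| Provision | Non-serious AE | SAE |
|---|---|---|
| 8.1.1 definition | outside | outside |
| 8.3 start rule | not yet reportable | only if caused by a protocol procedure |
| 8.3 end rule | implies reporting | implies reporting |
| Appendix E | starts at study drug, so not collected | collected from consent |
| 5.3.1 and 7.1.1 | not evaluable | not evaluable |
| 11.3 | in denominator | in denominator |

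For non-serious AEs, every explicit start condition is treatment. For SAEs, section 8.3 and Appendix E disagree directly.

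**Step 3. Direction and size of the bias.** Let pE be the true rate in the treated arm, pC the true background rate on observation, and c the share of control patients with an event in whom it is recorded. The documents give none of these, so the values below are assumptions.

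- By arm, the recorded difference is pE − c·pC and the true difference is pE − pC. The overstatement is (1 − c)·pC.
- Pooled at 1:1, the recorded rate is (pE + c·pC) / 2. With c = 0 this is pE / 2.

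Overstatement of the by-arm excess, in percentage points:

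| pC (assumed) | c = 0 | c = 0.5 | c = 1 |
|---|---|---|---|
| 10% | 10 | 5 | 0 |
| 30% | 30 | 15 | 0 |
| 50% | 50 | 25 | 0 |

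Pooled rate with c = 0, using whole patients:

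- True 20%: 5/26 treated becomes 5/52 = 10%.
- True 50%: 13/26 becomes 13/52 = 25%.
- True 80%: 21/26 becomes 21/52 = 40%.

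Pooled rate with all control events recorded (c = 1) and a treated rate of 13/26 = 50%:

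- pC = 10%: (13 + 3) / 52 = 31%.
- pC = 30%: (13 + 8) / 52 = 40%.
- pC = 50%: (13 + 13) / 52 = 50%.

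A pooled table therefore misstates the treated rate whenever the arms differ, even with complete recording. A by-arm table leaves the treated rate intact and puts the error in the comparison.

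**Step 4. Cross-over.** Section 11.2 assumes a 2-month median progression-free survival in the control arm. If times are exponential (assumption), the share with an event by t months is 1 − 2^(−t/2). At the first 8-week scan, t = 8 / 4.345 = 1.84 and the share is 47%, about 12 of 26. At 6 months it is 1 − 2^(−3) = 87.5%, about 23 of 26. These are upper limits on cross-over, since some events are deaths and not every patient will cross over. Those who do become reportable under the narrow rules, but their events then reflect exposure to the combination, not background.

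**The case against.** A reader might infer that the observation arm will show almost no events, or that half of the phase II safety denominator can have no countable AE. The documents do not support that.

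- Section 8.3 names the last observation follow-up visit as an end of reporting, for AEs and again for SAEs. That makes sense only if such events are expected. The fair reading is an arm with a stated end and no stated start.
- Appendix E collects SAEs from consent, whatever the treatment.
- Section 8.1.1 also says that AEs include patient-reported events and clinically significant examination or laboratory findings. Observation patients have examinations and laboratory tests every 4 weeks.
- The visit list in section 6.2 names no AE assessment for treated patients either, so its silence does not separate the arms. The calendar also omits the observation laboratory tests and imaging that section 6.2 requires, so its silence on AEs is weak evidence.
- Patients who cross over become reportable.
- Dilution requires pooling, which section 11.3 does not state. The plan specifies no between-arm safety test, and the primary endpoint is unaffected.

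All of this stands, and it removes any claim of a control column that is empty by design. It does not remove the contradiction. An end without a start still leaves sites to choose, the SAE rule in Appendix E does not reach non-serious events, and visits at which events could be found do not make them recordable under section 8.1.1. The safety summaries that section 11.3 plans for all randomized patients still need control-arm data collected under one rule.

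**Conclusion.** The concern holds as an internal inconsistency with a predictable consequence. Followed literally, the rules leave non-serious AEs on observation uncollected before cross-over while those patients count in the denominator. Followed by intent, recording depends on how each site resolves the conflict. Either way the control column cannot be relied on.

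A by-arm comparison would overstate the combination's excess by the unrecorded part of the background rate: 0 to 30 points over assumed background rates of 10% to 30%, with the upper end requiring that nothing is recorded. A pooled table would show about half the treated rate if allocation is 1:1 and no control events are recorded. The allocation ratio, all event rates and the recording share are assumptions, so the direction is established and the size is not.

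**What to change.** 1. In section 8.1.1, define a phase II AE as any untoward medical occurrence from randomization onward, in either arm.
2. In section 8.3 and Appendix E, give randomization as the AE start for phase II, and reconcile their two SAE rules. Using one anchor also treats the interval between randomization and first dose in the same way in both arms.
3. In section 6.2 and the calendar, add AE assessment to the existing 4-weekly observation visits.
4. Align sections 5.3.1 and 7.1.1 with section 11.3, so that evaluability for toxicity and the safety population describe the same patients. State how experimental-arm patients who are never dosed are handled.
5. In section 11.3, tabulate phase II AEs by arm with time at risk, and report AEs after cross-over separately.

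The cost is wording in these sections, case report form pages for observation patients, and slightly more data entry at visits already held. No visits or patients are added. One limit remains: treated patients are seen every 2 weeks and observation patients every 4, so detection will still differ somewhat, and the safety report should say so.
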